5.0 DOCUMENT HISTORY

Document	Date of Issue	Summary of Change
Protocol Version 2.1	03.02.2013	1. Defined walking speed removed from inclusion criteria 2. Additional questionnaire on upper limb function added (AMSQ).
Protocol Version 2.0	28.03.2012	Formatted IMB specification
Original Protocol	02.01.2012	Not applicable

6.0 SYNOPSIS

Title of study	A double blind, randomized, placebo controlled, crossover study of the effectiveness of oral fampridine in improving upper limb function in progressive multiple sclerosis.
Name of sponsor/company	St. Vincent's University Hospital, Dublin
Phase of development	IV
Objectives	
Primary Aims: To assess the effect of treatment with fampridine in patients with secondary progressive MS (SPMS) or primary progressive MS (PPMS) with upper limb dysfunction (as defined by a 9-HPT time of between 15-90 seconds) and Kurtzke EDSS scores in the range 4.0-7.0 on upper limb function assessed by the nine-hole peg test (9-HPT) and the Jebson Taylor Hand Function Test (JTT).
 
Secondary aims: To assess the effect of treatment with fampridine on walking mobility assessed by the Timed 25 foot Walk (T25FW) and the Multiple Sclerosis Walking Scale (MSWS-12). To determine whether response or non-response to fampridine by the T25FW can be easily determined using self reported changes in the MSWS-12 alone within 4 weeks in the course of active therapy. To determine whether response or non-response to fampridine by the 9HPT or JTT can be easily determined using self reported changes in the DASH and AMSQ alone within 4 weeks on the course of active therapy. To determine whether any relation exists between improvement / lack of improvement on the T25FW and improvement/ lack of improvement on the 9-HPT or JTT. To examine the safety of fampridine in this patient population. To assess the impact of fampridine on health related quality of life in patients with multiple sclerosis (HRQOL) as measured by the SF-36 questionnaire.

Trial design	Crossover, randomized, double blind, placebo-controlled trial.
Key inclusion criteria	Patients with SPMS or PPMS, male and female, aged 18-70, who have Kurtzke EDSS scores in the range 4.0 to 7.0 inclusive and evidence of significant upper limb dysfunction as defined by a 9HPT of 15 – 90 seconds (dominant or non-dominant hand), will be recruited. Women in reproductive years will be required to use barrier or hormonal methods of contraception.

Key exclusion criteria	
Patients with a history of seizures, significant liver dysfunction, renal dysfunction, significant upper or lower limb arthritis or any other disorder including cognitive dysfunction which would affect the ability to accurately complete questionnaires and give full informed consent.
 
Patients with clinically significant upper limb ataxia or upper limb proprioceptive sensory loss, which in the opinion of the Clinician affect upper limb functional assessment. Patients concomitantly using medicinal products that are inhibitors of Organic Cation Transporter 2 (OCT2).
 
Patients on concurrent treatment with other medicinal products containing fampridine (4-aminopyridine). Pregnant or breast-feeding patients.

Number of subjects	80
Test product, dose and mode of administration	
Oral PR-Fampridine 10mg b.d
 
Oral Placebo one tablet b.d.

Duration of treatment	Two 8 week treatment periods
Statistical methods	Participants will be classified as to whether they are “responders” or “non-responders” by the 9-HPT and the T25FW according to defined criteria. Change in the MSWS-12, the MSIS-29 (physical) and the DASH and AMSQ in responders and non-responders will be examined by the Wilcoxin Signed Rank test to assess the significance of the mean differences between groups.
Sample size	80

7.0 ABBREVIATIONS

AE	Adverse event
AR	Adverse reaction
CA	Competent authority
CI	Chief investigator/Co-ordinating investigator
CRF	Case report form
CRO	Contract research organisation
CT	Clinical trial
CTA	Clinical trial authorization
DASH	Disabilities arm, shoulder, hand questionnaire
ECG	Electrocardiogram
EDSS	Expanded Disability Status Scale
EU	European Union
e-CRF	Electronic case report form
GCP	Good Clinical Practice
GP	General Practitioner
9-HPT	Hole Peg test
IB	Investigators brochure
ICF	Informed consent form
ICH	International Conference on Harmonisation
IEC	Independent Ethics Committee
IMB	Irish Medicines Board
IMP	Investigational medicinal products
IMPD	Investigational medicinal product dossier
HSE	Health Service Executive
JTT	Jebson Taylor Hand Function Test
MS	Multiple Sclerosis
MSIS-29	Multiple Sclerosis Impact Scale 29
MSWS-12	Multiple Sclerosis Walking Scale
OCT-2	Organic Cation Transporter 2
PI	Principal investigator
PIL	Patient/subject information leaflet
PPMS	Primary Progressive MS
REC	Research ethics committee
ROI	Republic of Ireland
SAE	Serious adverse event
SAR	Serious adverse reaction
SmPC	Summary of product characteristics
SOP	Standard operating procedure
SPMS	Secondary Progressive MS
SVUH	St. Vincent's University Hospital, [name]
SUSAR	Suspected unexpected serious adverse reaction
T25FW	Twenty-five foot timed walk

8.0 INTRODUCTION

8.1 BACKGROUND INFORMATION

Patients with secondary progressive MS (SPMS) and primary progressive MS (PPMS) have significant walking disability and impaired upper limb function due to repeated demyelination and axonal injury affecting the corticospinal pathways. In some patients this motor deficit may be predominantly due to demyelination resulting in motor conduction slowing and/or block which is potentially reversible by blocking potassium channels of demyelinated axons. Fampyra® (fampridine-PR) is a prolonged-release formulation of the active drug substance 4-aminopyridine {4-AP; fampridine [International Nonproprietary Name (INN)]. Fampridine is able to block certain voltage-gated K⁺ channels in neurons, particularly in demyelinated nerves. Blockade of repolarising K⁺ currents can increase synaptic transmission throughout the nervous system by increasing the duration of the presynaptic action potential. Demyelinated nerves lose their ability to effectively conduct action potentials and fampridine can help reverse this. This effect was demonstrated clinically in a proportion of multiple sclerosis (MS) patients who showed a significant improvement in motor function, specifically walking ability, with Fampyra treatment. Fampridine-PR 10 mg every 12 hours or twice daily (BID) was approved in Europe (20 July 2011) for this indication under the brand name of Fampyra®.

8.2 RATIONALE FOR THE STUDY

Treatment with fampridine (4-aminopyridine), a potassium channel blocker,^{1,2} has been shown to cause significant improvement in walking speed in one third of MS patients with motor disability.³⁻⁵ In those patients who respond, approximately a 25% improvement in walking speed was obtained with a self-reported 7 point improvement in the Multiple Sclerosis Walking Scale (MSWS-12), a patient-rated measure of walking quality and ability,^{6,7} in comparison to non-responding patients and placebo control subjects.

Pharmacologically, the K⁺ channel blocking properties of fampridine and its effects on action potential conduction in demyelinated nerve fiber preparations have been extensively characterized. At low concentrations that are relevant to clinical experience (in the range of 0.2 to 2 µM [18 to 180 ng/mL]), fampridine is able to block certain voltage-dependent K⁺ channels in neurons. It is this characteristic that appears to explain the ability of the drug to restore conduction of action potentials in some critically demyelinated nerve fibers. At higher (millimolar) concentrations, fampridine affects other types of K⁺ channels in both neural and non-neural tissues. Blockade of repolarising K⁺ currents may increase synaptic transmission throughout the nervous system by increasing the duration of the presynaptic action potential. A range of neurological effects consistent with increased excitability of nerve cells occurs with clinically relevant doses of fampridine.

Toxicology studies performed with fampridine included acute and repeated-dose toxicology studies, reproductive toxicity studies, genotoxicity studies, and carcinogenicity studies. Clinical signs evident after large, single, oral doses or repeated, lower, oral doses (and continuous intrathecal infusion in the dog) were similar in all species studied and were indicative of central nervous system activation (including tremors, convulsions, ataxia, dyspnea, dilated pupils, prostration, abnormal vocalization, increased respiration, excess salivation, gait abnormalities, and hyper- and hypo-excitability). These clinical signs are considered to represent exaggerated pharmacology of fampridine. It would appear that limiting toxicities would rule out any concerns regarding potential mutagenicity, carcinogenicity, or teratogenicity of fampridine. During the Fampyra development program, more than 1900 subjects were exposed to fampridine in 57 clinical studies. The most frequent treatment-related adverse events (AEs) reported with fampridine in subjects with MS, as well as other populations, including subjects

with spinal cord injury, may be broadly categorized as excitatory effects in the nervous system consistent with the K⁺ channel blocking activity of the compound in the nervous system. These AEs include dizziness, paresthesias, insomnia, balance disorders, anxiety, confusion, and seizure. In studies in MS patients, the following most frequent treatment-related AEs were also observed: urinary tract infection, asthenia, back pain, constipation, dyspepsia, and pharyngolaryngeal pain. At higher dose levels, more severe central nervous system AEs such as confusion and seizure have been seen. With the adoption of the 10 mg BID dose in extension studies, the rate of first seizure has been approximately 0.32 per 100 subject-years. This rate does not exceed the expected incidence of seizures in the MS population, particularly in the more advanced disease state with significant ambulatory disability¹⁸. However, patients were excluded from these studies if they had a history of seizure or evidence of epileptiform activity on a screening electroencephalogram. Seizures have been seen in the post marketing setting in the US although confounding factors such as seizure history and use of concomitant medications that have been associated with a seizure risk may have contributed to the occurrence of seizures in some patients. No new safety signal has been detected as of March 2011.

The FDA has recently approved Fampridine, a slow release preparation, for use in the MS patient population.⁸ It has also recently been approved in Europe (20th July 2011).¹⁷ Most studies of fampridine assessed timed walking over twenty-five feet and the Multiple Sclerosis Walking Scale-12 (MSWS-12).³⁻⁵ Deficits in arm and hand function are commonly found in patients with SPMS and PPMS and can have an impact in performing many activities of daily living. We propose to examine the efficacy of fampridine in upper limb function and in overall disease impact in a single centre, double blind, randomized, placebo-controlled, crossover study of patients attending St Vincent's University Hospital with significant walking and upper limb disability due to SPMS and PPMS.

9.0 STUDY OBJECTIVE

The objective of this study is to assess the affect of PR-fampridine medication compared to placebo for upper limb function in patients with progressive multiple sclerosis

9.1 PRIMARY OBJECTIVE

The primary objective is to assess the effect of treatment with oral PR-fampridine in patients with secondary progressive MS (SPMS) or primary progressive MS (PPMS) with upper limb dysfunction (as defined by a 9-HPT time of between 15-90 seconds) and Kurtzke EDSS¹⁴ scores in the range 4.0-7.0 on Upper limb function assessed by the nine-hole peg test (9-HPT) and the Jebson Taylor Hand Function Test (JTT). Scores of the MSIS-29 (physical), MSWS-12 and the Disabilities of the Arm, Shoulder and Hand Score (DASH)¹⁰ and the Arm Function in Multiple Sclerosis Questionnaire (AMSQ)¹⁹.

9.2 SECONDARY OBJECTIVE

Secondary objectives are:

To assess the effect of treatment with fampridine on walking mobility assessed by the Timed 25 foot Walk (T25FW) and the Multiple Sclerosis Walking Scale (MSWS-12)^{6,7}

To determine whether response or non-response to fampridine by the T25FW can be easily determined using self reported changes in the MSWS-12 alone within 4 weeks in the course of active therapy

To determine whether response or non-response to fampridine by the 9HPT or JTT can be easily determined using self reported changes in the DASH and AMSQ alone within 4 weeks on the course of active therapy

To determine whether any relation exists between improvement / lack of improvement on the T25FW and improvement/ lack of improvement on the 9-HPT or JTT.

To examine the safety of fampridine in this patient population

To assess the impact of fampridine on health related quality of life in patients with multiple sclerosis (HRQOL) as measured by the SF-36 questionnaire.

9.3 EXPLORATORY OBJECTIVES

None

9.4 PRIMARY AND SECONDARY/ EXPLORATORY ENDPOINTS/OUTCOME MEASURES

Primary endpoint:

The primary end point will be identifying an upper limb responder to fampridine defined as a patient with both of the two “on treatment” 9-HPT assessments (assessments 4 & 5 or 7 & 8) improving 20% from the average of the baseline assessments (1, 2 & 3).

Secondary endpoints:

A secondary measure of upper limb responsiveness will be defined as a 20% improvement in from baseline in the average time taken to complete all seven tasks on the JTT “on treatment” (assessments 4 & 5 or 7 & 8) compared with baseline assessments (assessments 1,2 & 3).

A mobility responder to Fampridine will be defined as a patient with both of the two “on treatment” T25FW assessments (assessments 4 & 5 or 7 & 8) being better than the maximum of any of the four “off treatment” assessments (assessments 1, 2, 3, & 9). Otherwise the patient will be deemed a non-responder.

The responders to the 9-HPT and/or JTT will be compared to the non-responders in relation to their changes in the DASH and AMSQ on treatment and off treatment at the baseline assessment. The change in the DASH and AMSQ in responders at Assessment 5 or 8 (week 10 or 20) will be compared to non-responders at that time-point.

Upper limb response will be examined at the end of treatment phase 1 and repeated at the end of the trial by comparing patients receiving active drug with those receiving placebo to assess any placebo effect and allow assessment of any residual beneficial effect on those who receive fampridine in treatment phase 1 and then switch to placebo in treatment phase 2. Response will again be considered as a 20% improvement in the 9HPT in the active treatment group compared with placebo and a 20% improvement from baseline in the time taken to complete all seven tasks in the JTT. See earlier comment

The responders to the T25FW will be compared to the non-responders in relation to their changes in the MSWS-12 on treatment and off treatment at the baseline assessment. The change in the MSWS-12 in responders at Assessment 5 or 8 (week 10 or 20) will be compared to non-responders at that time-point.

The patients’ scores on the MSIS-29 (physical) and SF-36 will be examined in relation to the objective changes (responder/non-responder) in the 9-HPT, JTT and the T25FW.

10.0 TRIAL DESIGN

[figure not shown]
10.1 GENERAL CONSIDERATIONS

This will be a single centre, phase IV, double blind, randomized, placebo controlled, crossover study on the effectiveness of oral Fampridine-PR 10mg tablets BID on upper limb function for patients with progressive multiple sclerosis.

The trial will consist of a two week run in period followed by an eight week treatment period where enrolled subjects will be randomised to receive either study drug or placebo in a double blinded manner. This will be followed by a two-week wash out period followed by a further eight-week study period using active drug or placebo. There will be a two-week washout period at the end of the study. The total period of the study will be 22 weeks.

Each subject will attend for a screening visit and 8 assessment visits (total number of visits, 9).

Figure 1: Study Schema

10.2 SELECTION OF STUDY POPULATION

Overall description of trial subjects

The study will recruit male and female patients between the ages of 18 – 70 years with clinically definite primary or secondary progressive multiple sclerosis. Patients will be identified in and recruited from the multiple sclerosis clinics in St. Vincent's University Hospital, Dublin, Ireland.

Inclusion criteria

To be eligible for inclusion, each subject must meet each of the following criteria at Screening (Visit 1) and must continue to fulfill these criteria at Baseline (Visit 2).

Subjects must be able and willing to give written informed consent and to comply with the requirements of this study protocol

Subjects must be diagnosed with clinically definite SPMS or PPMS and be judged to be in generally good health by the investigator based upon the results of the medical history, laboratory tests (liver and renal function), physical examination, 12-lead electrocardiogram performed during Screening

Subjects must be Male or female aged 18-70 at baseline

Kurtzke EDSS scores in the range 4.0 to 7.0 inclusive

Evidence of significant upper limb dysfunction as defined by a 9HPT of 15 – 90 seconds (dominant or non-dominant hand)

Female subjects with reproductive capabilities must have a negative serum pregnancy test at baseline and agree to using an acceptable form of contraception for the duration of the study (barrier, coil or oral contraceptives only).

Exclusion criteria

Subjects are excluded from the study if any of the following criteria are met at Screening (Visit 1) or at Baseline (Visit 2):

- Allergy/sensitivity to study medications or their ingredients
- Female subjects who are pregnant or breast-feeding or considering becoming pregnant during the study.
- Subjects unable to provide written informed consent
- Subjects with a history of epilepsy or previous seizures (including provoked seizures).
- Subjects who have a history of drug or alcohol use that, in the opinion of the investigator, would interfere with adherence to study requirements.
- Subjects with an AST or ALT ≥ 3 x ULN on liver function tests
- Subjects have clinically significant ECG findings as judged by the investigator, in particular evidence of a cardiac conduction defect.
- Significant upper or lower limb arthritis as considered by the investigator to interfere with study assessments.
- Significant cognitive impairment as considered by the investigator to interfere with study assessments

- Subjects with clinically significant upper limb ataxia considered by the investigator to interfere with ability to complete study outcome measures.
- Patients with mild, moderate or severe renal impairment (creatinine clearance <80ml/min) measured by 24-hour urine collection or estimated by the Cockcroft and Gault formula
- Subjects concomitantly using medicinal products that are inhibitors of Organic Cation Transporter 2 (OCT2) for example cimetidine
- Concurrent treatment with other medicinal products containing fampridine (4- aminopyridine)

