10.3 STUDY ASSESSMENTS AND PROCEDURES

Patients likely to fulfill the inclusion criteria and not meet any exclusion criteria will be provided with information on the study and invited to attend a subsequent screening visit. Only patients who have signed the informed consent form will participate in any study related procedures including blood testing and ECG.

At screening visit (Assessment 1) subjects will have a physical examination and an EDSS score rated. Blood samples will be taken for renal and liver function and a baseline ECG performed. Patients will complete a nine-hole peg test and a JTT. T25FW will be recorded and the patients invited to complete the MSIS-29, MSWS-12, DASH, AMSQ and SF-36 questionnaires. Patients with any abnormalities on ECG, blood tests will not be invited to a baseline visit and considered a screening failure.

Following screening visit subjects fulfilling the inclusion / exclusion criteria will have two baseline visits (Assessments 2 and 3) at the end of week one and end of week two. The 9-HPT, JTT and T25FW will be repeated to allow for training effects. Patients will be randomised to group A or group B and receive study medication or placebo at baseline visit based on their blinded randomisation (Assessment 3).

The first treatment period will be from the start of week 3 until the end of week 10. Patients will have an assessment at the end of week 6 (Assessment 4) and the end of week 10 (Assessment 5). At both assessments patients will have the 9-HPT, JTT, T25FW, MSIs-29, MSWS-12, DASH, AMSQ and SF-36 recorded. Weeks 11 and 12 will be a washout period (no drug/placebo). Assessment 6 will occur at the end of week 12 and will include recording of 9-HPT, JTT, T25FW, MSIs-29, MSWS-12, DASH, AMSQ and SF-36. Any adverse events will be recorded at each visit as will the use of concomitant medications.

The second treatment period will begin at the start of week thirteen with groups A and B switching study drug / placebo in a blinded manner. The second treatment period will continue for a further 8 weeks with two more assessments at week 16 (Assessment 7) and week 20 (Assessment 8). At both of these assessments subjects will complete the 9-HPT, JTT, T25FW, MSIs-29, MSWS-12, DASH, AMSQ and SF-36. At the end of week 20 and EDSS score will be recorded. Any adverse events will be recorded at each visit as will the use of concomitant medications.

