There will be a final washout period (weeks 21 and 22) after which a final visit (assessment 9) will occur and subjects once again completing 9-HPT, JTT, T25FW, MSIs-29, MSWS-12, DASH, AMSQ and SF-36 and having an EDSS score recorded. Once again adverse events will be recorded.

(See Schedule of Events, page 15)

Figure 2: Schedule of events

Assessment	1 Screening Visit	2 Baseline Visit	3 Base - line Visit	4 Rx Phase 1	5 End of Rx Phase 1	6 End Wash- out phase	7 Rx Phase 2	8 End of Rx Phase 2	9 End of 2 week washout
Time (start/end week)	week 1 (start)	week 1 (end)	week 2 (end)	week 6 (end)	week 10 (end)	week 12 (end)	week 16 (end)	week 20 (end)	week 22 (end of trial)
Informed consent	X								
Serum pregnancy test (female subjects)	X								
EDSS	x							X	X
ECG	X								
Receiving Medication	No	No	Start drug	Continu e drug	Stop drug	Start drug	Continu e drug	Stop drug	Wash out
9- HPT	x	x	x	x	x	x	x	x	X
JTT	x	x	x	x	x	x	x	x	X
T25FW	x	x	x	x	x	x	x	x	X
MSIS-29	x		x	x	x	x	x	x	X
MSWS-12	x		x	x	x	x	x	x	X
DASH	x		x	x	x	x	x	x	X
AMSQ	x		x	x	x	x	x	x	x
SF-36	X		X	X	X	X	X	X	X
Adverse event recording				X	X	X	X	X	X
Concomitant medication recording	X		X	X	X	X	X	X	X
Study Drugs dispensed			X			X			

Description of Study Assessments

Medical and Surgical History will be recorded with particular attention on the diagnosis of MS, duration of MS and MS subtype.

Demographics

The date of birth, gender and race will be recorded.

Physical Examination

The complete physical examination will include the evaluation of the neurological system and a recording of the EDSS score and T25FW.

ECG Test

One ECG including a 12-lead examination will be performed at Screening (assessment 1).

Abnormal findings will be noted for clinical significance. The report will be signed by the investigator.

Clinical Laboratory Tests

1. Haematology: haemoglobin, WBC, RBC, platelet count
2. Biochemistry: creatinine or creatinine-clearance, sodium, potassium, liver function tests
3. All laboratory results will be reviewed and the reports signed by the investigator who will record in the CRF whether they are normal, abnormal but not clinically significant, or abnormal and clinically significant.

Pregnancy Tests

Serum pregnancy test and urine pregnancy test in women of childbearing potential will be performed.

Concomitant Medication

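### As written, group B can start fampridine at Assessment 6 some 70 to 84 days after its last scheduled pregnancy test, because the urine test has no visit (minor, patient safety)

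*Combined protocol and SAP*

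**What the plan says.** **Eligibility (10.2).** A woman able to conceive "must have a negative serum pregnancy test at baseline". The lead-in to the inclusion list treats screening as Visit 1 and adds that subjects "must continue to fulfill these criteria at Baseline (Visit 2"). Pregnancy is an exclusion at either of those visits.

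**Visits (10.3).** After screening, subjects "will have two baseline visits (Assessments 2 and 3) at the end of week one and end of week two". They are randomised and "receive study medication or placebo at baseline visit based on their blinded randomisation (Assessment 3").

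**Schedule (10.3, Figure 2).** The row "Serum pregnancy test (female subjects") has a single mark, under Assessment 1. The row "Study Drugs dispensed" has two marks, under Assessments 3 and 6. There is no urine test row.

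**Description of assessments (10.3).** Under the pregnancy test heading: "Serum pregnancy test and urine pregnancy test in women of childbearing potential will be performed". No visit is named for either test.

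**Second dispensing visit (10.3).** "Assessment 6 will occur at the end of week 12 and will include recording of 9-HPT", followed by the other functional tests and the questionnaires. Adverse events and concomitant medication are also recorded. No pregnancy test is listed.

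**Sequence (10.3.3, Table 1).** Group B receives placebo first and fampridine second.

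**The concern.** In a two-period crossover the second dispensing visit is the first active exposure for half the subjects. This protocol wants pregnancy ruled out before drug is started: it excludes pregnant women, asks for a negative serum test, and makes pregnancy a mandatory reason to stop (10.5). The schedule applies that check close to first exposure only for group A. For group B the placed test lies before period 1, so a full placebo period and a washout pass before fampridine is started.

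The promised urine test could fill the gap, but without a visit the site cannot tell when to do it and a monitor cannot tell whether it was missed. At stake is an avoidable fampridine exposure in an unrecognised pregnancy. Nothing in the efficacy analysis depends on this.

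**Working it through.** **Calendar check.** Run-in, treatment, washout, treatment, washout: 2 + 8 + 2 + 8 + 2 = 22 weeks, which matches the total in 10.1.

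**Days, taking the start of week 1 as day 0 (10.3 and Figure 2).**
- Assessment 1, start of week 1: day 0
- Assessment 2, end of week 1: day 7
- Assessment 3, end of week 2: day 14, first dispensing
- Assessment 5, end of week 10: day 70, end of period 1
- Assessment 6, end of week 12: 12 × 7 = day 84, second dispensing

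**Interval = day fampridine starts − day of the last placed test.** Group A starts at day 14 and group B at day 84.

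| Serum test taken at | Group A | Group B |
|---|---|---|
| Assessment 1 (Figure 2) | 14 − 0 = 14 days | 84 − 0 = 84 days |
| Assessment 2 (10.2, read as Visit 2) | 14 − 7 = 7 days | 84 − 7 = 77 days |
| Assessment 3 (10.2, read as the dispensing baseline visit) | 14 − 14 = 0 days | 84 − 14 = 70 days |

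Figure 2 alone gives 84 days. The 70-day end requires reading *baseline* in 10.2 as Assessment 3. With a test at Assessment 6 the group B interval is 84 − 84 = 0 days.

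**Which visit is *baseline*?** Within 10.2, Screening and Baseline are different visits. In 10.3, Assessments 2 and 3 are the baseline visits, yet the ECG taken at screening is called a baseline ECG. In 9.4, Assessments 1, 2 and 3 together form the baseline for the primary endpoint. The term is therefore used for any of the three.

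**Scale (assumptions, not in the documents).** Group B is 40 of the planned 80 (13.2). The number of women of childbearing potential is not given. Assume 5% to 30%: 40 × 0.05 = 2 to 40 × 0.30 = 12 in group B, and 80 × 0.05 = 4 to 80 × 0.30 = 24 overall. Assume 1% to 10% pregnancies per woman-year on the required contraception. Expected pregnancies in group B during the gap:
- low: 2 × 0.01 × 70/365 = 0.004
- high: 12 × 0.10 × 84/365 = 0.28

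**The case against.** **A reader might infer that 10.2 and Figure 2 contradict each other on the serum test.** The documents do not support that. Because 9.4 counts Assessment 1 among the baseline assessments and 10.3 has a baseline ECG at screening, a serum test at Assessment 1 can fairly be called a baseline test. The separate labels in 10.2 leave an ambiguity to clear up, no more. Reading it this way also gives group B the longest interval, 84 days.

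**A reader might infer that group B would go untested before fampridine.** That is not shown either. The undated urine test may have been meant as the check before dispensing. Figure 2 is not exhaustive (it has no row for the blood tests that 10.3 requires), and the study schema (Figure 1) was not visible in the copy reviewed. The 70 to 84 days describe what the text and Figure 2 schedule, not what would happen at the site.

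**Re-test frequency is partly a matter of preference.** No section sets a maximum interval from test to exposure. Group A also takes fampridine up to day 70 with no placed re-test, by then 70 − 14 = 56 to 70 − 0 = 70 days after its last test. This is fair, and nothing here asks for testing during treatment. The point is narrower: it concerns the check before *first* active exposure, which the plan places for group A and not for group B.

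**The safeguards are real.** Contraception is required throughout, women considering pregnancy are excluded (10.2), subjects are seen at Assessments 4, 5 and 6, pregnancy leads to withdrawal (10.5) and is followed to outcome (12.6), and 8.2 plays down concern about teratogenicity. These lower the risk. They do not detect an unrecognised pregnancy on the day group B first receives fampridine.

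**Conclusion.** The point holds as a minor, inexpensive patient-safety improvement. In the text and Figure 2 the serum test is the only pregnancy test tied to a visit, and that visit is Assessment 1, 2 or 3 depending on how *baseline* is read. On each of these readings group B can start fampridine at least 10 weeks after its last scheduled test: 70 to 84 days, against 0 to 14 for group A. These intervals rest only on the protocol's calendar.

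The absolute risk is low. The range of 0.004 to 0.28 expected pregnancies rests wholly on assumed rates. Its upper end combines the worst value of each input and treats every conception as going unrecognised until dispensing, so it is best read as well below one. The finding does not show that women would be exposed while pregnant, and no effect on efficacy is claimed.

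**What to change.** 1. **Figure 2:** add a urine pregnancy test row for women of childbearing potential, marked at Assessment 6, and at Assessment 3 unless the serum test is done there. Test both groups at Assessment 6, since visit staff are blinded.
2. **10.3:** dispense at those visits only after a negative result. If positive, withhold drug and confirm by serum. A confirmed pregnancy at Assessment 3, before randomisation, makes the subject ineligible; at Assessment 6, withdraw under 10.5 and notify under 12.6.
3. **10.2:** state which assessment *baseline* means for the serum test, and mark it there in Figure 2. This is a clarification only. If serum at Assessment 3 was intended, keep it and do not replace it with urine.

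**Cost.** One or two urine tests per eligible woman at visits already scheduled. Under the assumed 5% to 30% share this is 4 to 24 tests at Assessment 6 only, or 2 × 4 = 8 to 2 × 24 = 48 at both visits. The amendment must go to the ethics committee (19.0), with further approval under 19.3 if it is classed as substantial. There is no extra visit and no change to sample size, blinding or analysis.
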